5.9 Prior and Concomitant Therapies and Medications

5.9.1 Prior and Concomitant COPD Medications

All prior therapies for COPD taken in the 3 months prior to the first study treatment administration and all concomitant COPD therapies will be recorded in the eCRF, with the medication, dose, route and start and stop date(s) and time(s) clearly recorded to document all required washout periods and compliance with the Inclusion and Exclusion Criteria.

Verona Pharma plc CONFIDENTIAL Page 27 of 66

The following therapies are restricted or prohibited during the study as indicated:

- Oral therapies for COPD (e.g. oral steroids, theophylline, and roflumilast) are not allowed in the 3 months prior to Screening and throughout the study. Inhaled steroids may continue during the study at a maintenance dose
- Terbutaline is not allowed beginning the day prior to Screening
- Pulmonary rehabilitation programs should not be started or completed during participation in the study, although an ongoing maintenance program is acceptable in accordance with Exclusion Criterion #9
- Oxygen therapy and non-selective oral β-blockers are Exclusion Criteria and are not to be used at any time during the study
- Oral mucolytics and ocular β-blockers are allowed
- All long acting (once or twice daily) bronchodilators (long acting muscarinic antagonists [LAMA], long acting β₂-agonists [LABA], or combinations with an inhaled steroid) are to be discontinued prior to the Screening visit and are not allowed during the study. The withhold period prior to Screening is as follows:
 - Once daily bronchodilators at least 48 hours prior
 - o Twice daily bronchodilators at least 24 hours prior
- Patients taking LAMAs and LABAs should be placed on short acting bronchodilators (e.g. salbutamol/albuterol, ipratropium or Combivent®) as per the discretion of the Investigator. These can be dosed on a regularly scheduled basis or as needed.
- Patients taking inhaled corticosteroids may continue their medication only if the dose is stable from at least 4 weeks prior to Screening and is expected to remain stable.
- Patients taking LABA/inhaled steroid combination products should be prescribed the
 inhaled steroid at the same or equivalent dose contained in the combination product to allow
 continuation of steroid use regularly throughout the study whilst stopping the LABA
 component. Inhaled steroid medication should be procured via prescription for patients

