 requiring its use; it will not be supplied by the Sponsor.
- No scheduled use of salbutamol/albuterol or ipratropium is allowed during the 3-day treatment periods; but may be used as a rescue medication (see Section 5.10). Salbutamol/albuterol and ipratropium (or Combivent®) must be withheld for at least 8 hours prior to spirometry (per below), and this is to be confirmed in the eCRF at the start of each treatment period. If this withhold is not met, the patient should be rescheduled for a repeat visit within permitted windows. Short acting bronchodilators should be withheld as follows:
 - o 8 hours prior to pre-reversibility spirometry for Screening
 - o 8 hours prior to pre-dose spirometry for Day 1, Day 2 and Day 3
 - Post dose:
 - Day 1 until after +12 hours spirometry
 - Day 2 until after + 12 hours spirometry
 - Day 3 until after + 24 hours spirometry (Day 4 morning)

If following the above requirements provide inadequate symptom control, patients should contact the Investigator.

Verona Pharma plc CONFIDENTIAL Page 28 of 66

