5.10 Rescue Medications

Short acting bronchodilators may be used as rescue medication. Rescue medication will be sourced by the study center and dispensed at the Screening visit. Rescue medication use during each treatment period must be separately documented on the eCRF (medication, dose, route, date and time of each administration). Protocol procedures must still continue even if rescue medication has been taken. Salbutamol/albuterol is to be used for primary rescue use.

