14.2 Tiotropium/Olodaterol Prescribing Highlights and Instructions for Use

Note: The information below is excerpted from the US package insert for tiotropium/olodaterol. Full prescribing information in the US is available at:

 $\underline{http://docs.boehringer-ingelheim.com/Prescribing\%20Information/PIs/Stiolto\%20Respimat/stiolto.pdf}$

Full prescribing information in the UK is available at:

http://www.spioltorespimatpi.uk

HIGHLIGHTS OF PRESCRIBING INFORMATION
These highlights do not include all the information needed to use
STIOLTO RESPIMAT safely and effectively. See full prescribing
information for STIOLTO RESPIMAT.

STIOLTO* RESPIMAT* (tiotropium bromide and olodaterol) inhalation spray, for oral inhalation use Initial U.S. Approval: 2015

WARNING: ASTHMA-RELATED DEATH See full prescribing information for complete boxed warning.

- Long-acting beta₂-adrenergic agonists (LABA) such as olodaterol, one of the active ingredients in STIOLTO RESPIMAT, increase the risk of asthma-related death. (5.1)
- A placebo-controlled study with another long-acting betagadrenergic agonist (salmeterol) showed an increase in asthmarelated deaths in patients receiving salmeterol. (5.1)
- This finding of an increased risk of asthma-related death with salmeterol is considered a class effect of LABA, including olodaterol, one of the active ingredients in STIOLTO RESPIMAT. The safety and efficacy of STIOLTO RESPIMAT in patients with asthma have not been established. STIOLTO RESPIMAT is not indicated for the treatment of asthma. (4, 5.1)

-INDICATIONS AND USAGE-

STIOLTO RESPIMAT is a combination of tiotropium, an anticholinergic and olodaterol, a long-acting beta;-adrenergic agonist (LABA) indicated for: The long-term, once-daily maintenance treatment of airflow obstruction in patients with chronic obstructive pulmonary disease (COPD) (1.1)

Important limitations

- STIGLTO RESPIMAT is NOT indicated to treat acute deterioration of COPD. (1.2)
- STIOLTO RESPIMAT is NOT indicated to treat asthma. (1.2)

-DOSAGE AND ADMINISTRATION-

- For oral inhalation only.
- Two inhalations of STIOLTO RESPIMAT once-daily at the same time of day. (2)

--- DOSAGE FORMS AND STRENGTHS-

Inhalation spray: Each actuation from the mouthpiece contains 3.124 mcg tiotropium bromide monohydrate, equivalent to 2.5 mcg tiotropium, and 2.736 mcg olodaterol hydrochloride, equivalent to 2.5 mcg olodaterol.

Two actuations equal one dose. (3)

-CONTRAINDICATIONS-

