- All LABAs are contraindicated in patients with asthma without use of a long-term asthma control medication. (4) STIOLTO RESPIMAT is not indicated for the treatment of asthma. (1.2)
- Hypersensitivity to tiotropium, ipratropium, olodaterol, or any component of this product. (4)

-WARNINGS AND PRECAUTIONS-

- LABA increase the risk of asthma related death. (5.1)
- Do not initiate STIOLTO RESPIMAT in acutely deteriorating COPD patients. (5.2)
- Do not use for relief of acute symptoms. Concomitant short-acting betagagonists can be used as needed for acute relief. (5.2)
- Do not exceed the recommended dose. Excessive use of STIOLTO RESPIMAT, or use in conjunction with other medications containing LABA can result in clinically significant cardiovascular effects and may be fatal. (5.3)
- Immediate hypersensitivity reactions: Discontinue STIOLTO RESPIMAT at once and consider alternatives if immediate hypersensitivity reactions, including angioedema, bronchospasm, or anaphylaxis, occur. (5.4)
- Life-threatening paradoxical bronchospasm can occur. Discontinue STIOLTO RESPIMAT immediately. (5.5)
- Use with caution in patients with cardiovascular or convulsive disorders, thyrotoxicosis, or sensitivity to sympathomimetic drugs. (5.6, 5.7)
- Worsening of narrow-angle glaucoma may occur. Use with caution in patients with narrow-angle glaucoma and instruct patients to consult a physician immediately if this occurs. (5.8)
- Worsening of urinary retention may occur. Use with caution in patients with prostatic hyperplasia or bladder-neck obstruction and instruct patients to consult a physician immediately if this occurs. (5.9)
- Be alert to hypokalemia and hyperglycemia. (5.11)

-ADVERSE REACTIONS-

The most common adverse reactions (>3% incidence and more than an active control) were nasopharyngitis, cough, and back pain.

To report SUSPECTED ADVERSE REACTIONS, contact Boehringer Ingelheim Pharmaceuticals, Inc. at [contact] or [contact] TTY, or FDA at [name] or www.fda.gov/medwatch.

-DRUG INTERACTIONS-

- Other adrenergic drugs may potentiate effect. Use with caution. (5.3, 7.1)
- Xanthine derivatives, steroids, diuretics, or non-potassium sparing diuretics may potentiate hypokalemia or ECG changes. Use with caution. (7.2, 7.3)
- MAO inhibitors, tricyclic antidepressants, and drugs that prolong QTc interval may potentiate effect on cardiovascular system. Use with extreme caution. (7.4)

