- Beta-blockers may decrease effectiveness. Use with caution and only when medically necessary. (7.5)
 Anticholinergics: May interact additively with concomitantly used
- Anticholinergics: May interact additively with concomitantly used anticholinergic medications. Avoid administration of STIOLTO RESPIMAT with other anticholinergic-containing drugs. (7.6)

-USE IN SPECIFIC POPULATIONS-

Patients with moderate to severe renal impairment should be monitored closely for potential anticholinergic side effects. (2, 8.7)

See 17 for PATIENT COUNSELING INFORMATION, Medication Guide, and Instructions for Use.

Revised: 6/2016

Instructions for Use

Tiotropium bromide and olodaterol inhalation spray

In the US: **STIOLTO**[®] **RESPIMAT**[®] (sti-OL-to-RES peh mat) (default name used below)

In the UK: **SPIOLTO**[®] **RESPIMAT**[®] (spi-OL-to-RES peh mat)

For Oral Inhalation Only

Do not spray STIOLTO RESPIMAT into your eyes.

Read these Instructions for Use before you start using STIOLTO RESPIMAT and each time you get a refill. There may be new information. This leaflet does not take the place of talking to your doctor about your medical condition or your treatment.

You will need to use this inhaler ONCE A DAY, at the same time each day. Each time you use it take TWO PUFFS.

Do not turn the clear base before inserting the cartridge.

How to store your STIOLTO RESPIMAT inhaler

- Store STIOLTO RESPIMAT at room temperature 68°F to 77°F (20°C to 25°C).
- Do not freeze your STIOLTO RESPIMAT cartridge and inhaler.
- If STIOLTO RESPIMAT has not been used for more than 3 days, release 1 puff towards the ground.
- If STIOLTO RESPIMAT has not been used for more than 21 days, repeat steps 4 to 6 under the "Prepare for first use" until a mist is visible. Then repeat steps 4 to 6 three more times.
- Keep your STIOLTO RESPIMAT cartridge and inhaler out of the reach of children.

How to care for your STIOLTO RESPIMAT inhaler

• Clean the mouthpiece, including the metal part inside the mouthpiece, with a damp cloth or tissue only, at least once a week. Any minor discoloration in the mouthpiece does not affect your STIOLTO RESPIMAT inhaler.

When to get a new STIOLTO RESPIMAT inhaler

• Your inhaler contains 60 puffs (30 doses) if used as indicated (2 puffs once daily). If you have a sample, your inhaler contains 28 puffs (14 doses) if used as indicated (2 puffs once daily).

[figure not shown]
- The dose indicator shows approximately how much medicine is left.

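### Ipratropium is allowed as rescue while every patient takes tiotropium/olodaterol, against the advice in the protocol's own US label excerpt and with no reason given

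*Protocol*

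**What the plan says.** Section 5.9.1 of the protocol stops routine use of the two short-acting drugs in the treatment periods but keeps both for rescue: "No scheduled use of salbutamol/albuterol or ipratropium is allowed during the 3-day treatment periods; but may be used as a rescue medication". Section 5.10 is wider: "Short acting bronchodilators may be used as rescue medication". It sets an order, "Salbutamol/albuterol is to be used for primary rescue use", but excludes no member of the class. In Section 5.9.1, in the advice for patients coming off long-acting agents, the class is illustrated as "short acting bronchodilators (e.g. salbutamol/albuterol, ipratropium or Combivent". SAP Section 12 repeats the class wording and the order.

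In these same periods every patient takes open-label tiotropium/olodaterol each morning (Sections 3.1 and 5.1). Section 5.2.2 points to Section 14.2 for that product, where the source is given: "The information below is excerpted from the US package insert for tiotropium/olodaterol". Under Drug Interactions the excerpt says "Avoid administration of STIOLTO RESPIMAT with other anticholinergic-containing drugs", because anticholinergic effects may add. Under Warnings and Precautions it says "Concomitant short-acting betagagonists can be used as needed for acute relief" (the garbled word is beta2-agonists).

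The synopsis puts patients on ipratropium and salbutamol/albuterol, regularly or as needed, over the whole study with the treatment periods excepted.

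**The concern.** As written, a patient who took tiotropium that morning may be given a second anticholinergic that the protocol's own product information advises avoiding. A rescue drug that the same excerpt accepts is at hand and is already the primary choice. None of Sections 1.2, 3.2, 5.4, 5.9.1 and 5.10, or SAP Section 12, says why ipratropium is kept. By contrast, the softer label caution on beta-blockers does have a counterpart, in the bar on non-selective oral beta-blockers (Exclusion 15).

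The synopsis adds to the uncertainty. Taken literally, it rules out as-needed use of both drugs during the treatment periods, which Sections 5.9.1 and 5.10 allow. Staff at different centers could apply different rules.

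What is at stake is avoidable additive anticholinergic exposure in a few patients, together with a clear instruction to sites.

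**Working it through.** No figure in the plan depends on this rule, so the main check is to set the texts side by side.

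1. **Is ipratropium permitted?** Yes. Section 5.9.1 names it as rescue for the 3-day periods.
2. **Is Combivent permitted?** Arguably. Section 5.10 allows the class and Section 5.9.1 lists Combivent in the class, but in the context of patients stopping long-acting drugs. It is nowhere named as treatment-period rescue.
3. **Is ipratropium second-line?** This is an inference from salbutamol/albuterol being the primary rescue drug; the documents do not use the term.
4. **How strong is the label advice?** It sits under Drug Interactions. The contraindications in the excerpt concern asthma and hypersensitivity, not use with other anticholinergics. For other adrenergic drugs the excerpt advises caution, which is weaker than its advice to avoid anticholinergics.
5. **Who remains at risk?** Exclusion 4 removes intolerance or hypersensitivity to ipratropium. Exclusion 19 removes narrow-angle glaucoma, symptomatic prostatic hyperplasia and bladder-neck obstruction. Exclusion 13 removes uncontrolled renal, urological and ophthalmic disease that the investigator considers clinically significant. It sets no creatinine limit, although the label excerpt asks for close monitoring of anticholinergic effects in moderate to severe renal impairment.

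The only arithmetic is the time left open by the withhold rules in Section 5.9.1. Short-acting drugs are barred until after the 12-hour spirometry on Days 1 and 2, for 8 hours before the next pre-dose spirometry, and on Day 3 until after the 24-hour spirometry. Assume that pre-dose spirometry is done at the time of the morning dose:

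- Each of the Day 1 and Day 2 evenings: 24 − 12 − 8 = 4 h.
- Per treatment period: 2 × 4 = 8 h, and 8/72 = 11% of the 72 h.
- Day 3: none before the 24-hour spirometry.

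These are approximate. Doses may move by 30 minutes (Section 5.4.2) and the 12-hour spirometry by 10 minutes (Sections 6.3.1.3 and 6.3.2.3). The Day 1 window can therefore shift by 30 + 10 = 40 minutes. The Day 2 window depends on two movable doses and can shift by 30 + 30 + 10 = 70 minutes. Time 0 is also the end of nebulization, which may last up to 10 minutes (Section 5.4.2.1), so a finer figure is not warranted. Nor do the windows cap actual use: "Protocol procedures must still continue even if rescue medication has been taken".

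SAP Section 12 expects low rescue use, defined as under 10% of patients, without saying whether that is overall or per treatment. Neither document gives a rate for ipratropium rescue.

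**The case against.** The case for leaving the text alone has substance. The protocol puts salbutamol/albuterol first, keeps patients resident, records each rescue dose by drug and time, and reproduces the label advice for the investigator who must choose a second agent. What is left is an occasional, supervised option that lacks a justifying sentence. That is fair as to size, and it is why the point is minor. It does not supply the missing reason.

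The label also carries cautions in the other direction. It advises care with additional adrenergic drugs and alertness to hypokalemia and hyperglycemia. All patients take olodaterol, and Section 1.2 reports heart-rate increases with RPL554, though at 12 to 24 mg, above the doses used here. A salbutamol-only rule concentrates repeat rescue in that class. This stands as a real cost of the change. The label still ranks the two, advising avoidance for one class and caution for the other.

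Ipratropium may also be resumed after the 24-hour spirometry on Day 4, about a day after the last tiotropium dose, and Section 3.2 gives tiotropium a terminal half-life of 5 to 6 days. Some overlap is therefore possible between periods. Section 3.2 also says that the bronchodilator effect has gone before then, and the documents offer nothing further with which to weigh residual exposure. The point is confined to days on which tiotropium/olodaterol is given.

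A reader might infer that the protocol breaches a contraindication. The excerpt does not say so, and the UK product information is not reproduced, so nothing can be said about it.

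**Conclusion.** The point holds as a minor patient-safety and clarity matter. The treatment-period rescue rule permits an anticholinergic that the protocol's own US label excerpt advises avoiding, gives no reason, and does not match the synopsis. Permitted exposure is small: nominally about 8 of 72 h per period, in a trial that expects few patients to need rescue at all. That figure rests on pre-dose spirometry being done at dose time and on the withhold rules being followed. The actual frequency of ipratropium rescue is unknown.

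A reader might also infer that ipratropium rescue distorts the comparison of RPL554 with placebo. The documents do not support that from this rule. It is identical in all three treatments, and the withhold rules bar short-acting drugs for 8 h before the Day 3 morning dose and throughout the primary measurement window. Rescue taken despite those rules would raise the same question whichever short-acting drug was used. No effect on bias, type I error, power or the primary endpoint is claimed.

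**What to change.** In Sections 5.9.1 and 5.10, state that during the treatment periods only salbutamol/albuterol is to be used as protocol rescue, and that ipratropium and Combivent are not, except as emergency treatment that the investigator judges necessary. Align the synopsis with this. Leave between-period ipratropium and its 8-hour withhold unchanged. The SAP does not govern prescribing, so Section 12 needs only matching wording if its rescue text is kept. If the sponsor prefers to retain ipratropium, a sentence giving the reason would also resolve the conflict.

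The change needs a few sentences and no extra patients, visits or procedures. Investigators lose routine second-line ipratropium, and repeat rescue becomes a beta-agonist on top of olodaterol. Existing monitoring gives reasonable cover: pulse and ECG are checked before each morning dose, Holter runs from Day 3, and patients are resident. No pulse or ECG check is scheduled within the Day 1 and Day 2 evening windows, so a check after repeat rescue would be unscheduled, which Section 6 allows.

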5.9.2 Other (non-COPD) Prior and Concomitant Medications

Patients may continue other prescribed non-respiratory therapies during the study that the Investigator considers to neither compromise subject safety nor affect study data. Such other prior prescription or non-prescription medications (medication, dose, route, treatment duration and indication) taken 3 months before the first study treatment administration must be recorded in order to confirm compliance with the Inclusion and Exclusion Criteria.

All concomitant medications must also be documented on the eCRF.

5.10 Rescue Medications

Short acting bronchodilators may be used as rescue medication. Rescue medication will be sourced by the study center and dispensed at the Screening visit. Rescue medication use during each treatment period must be separately documented on the eCRF (medication, dose, route, date and time of each administration). Protocol procedures must still continue even if rescue medication has been taken. Salbutamol/albuterol is to be used for primary rescue use.

5.11 Treatment Compliance

Study treatment administration will take place at the study center and will be administered by the Investigator or designated and trained study center personnel. The precise date and time of administrations shall be documented in the eCRF.

Verona Pharma plc CONFIDENTIAL Page 29 of 66

6 STUDY PROCEDURES AT EACH VISIT

The study will consist of the following:

- Screening will take place in the period between 7 and 14 days prior to the first study treatment administration. Screening procedures may be performed as a single visit or more than one visit. Since the Holter monitor is to be removed after 24 hours, patients will return one day after placement.
- Three treatment periods, each 3 days in duration and separated by 7 to 14 days (from last dose of study medication on Day 3 of each treatment period)
- An end of study visit between 4 and 10 days after the completion of Treatment Period 3 Eligible patients may be re-screened at the discretion of the Investigator.

Repeat, rescheduled, and unscheduled visits and procedures are permitted at the discretion of the Investigator.

The overall schedule of assessments at each visit is shown in Table 3 and the schedule of assessments on each day of each treatment period is shown in Table 4. Assessments are listed by visit in Section 1.1 to Section 6.4 and are described in Section 7.

Post-dose assessments should be performed in the following order: 1) ECG, 2) vital signs, 3) pharmacokinetic blood sample, 4) spirometry (prioritized on the timepoint).

Verona Pharma plc CONFIDENTIAL Page 30 of 66

Table 3 Overall Schedule of Assessments at Each Visit in RPL554-CO-204

Procedures	Screening	(7 to	End of Study			
Frocedures	14 to 7 days before Randomization	Day 1	Day 2	Day 3	Day 4	4 – 10 days after Day 4 o Treatment Period 3
Informed consent	X					
Demographics including height and weight	X					
Medical/surgical and disease history	X					
Eligibility criteria	X	X[a]				
Physical examination	X (Full)	X (Brief)			X (Brief)	X (Full)
Vital signs	X	X	X	X	X	X
Safety laboratory tests: hematology and biochemistry	X				X	X
Safety laboratory tests: urinalysis	X					X
Viral serology	X					
Alcohol breath test	X					
Serum pregnancy test (females of childbearing potential)	X					
Urine pregnancy test (females of childbearing potential)	X	X				X
Chest X-ray (or in last 12 months)	X					
12-lead ECG	X	X	X	X	X	X
24-hour Holter monitoring	X			X		
Spirometry: Reversibility test	X					
Spirometry: Study measurements		X	X	X	X	X
Whole body plethysmography training	X					
Whole body plethysmography		X		X		
Inhalation training (nebulizer and Respimat®)	X	X				
Randomization		X[a]				
Tiotropium/olodaterol and RPL554 or placebo dosing		X	X	X		
Pharmacokinetic sampling				X		
Dyspnea scale		X		X	X	
Prior/concomitant medications and therapies			Through	out the study	•	•
Adverse events				nout the study		

[a] Treatment Period 1 only

Table 4 Pre-dose and Post-dose Assessments on Each Day of Treatment Periods 1 to 3 in RPL554-CO-204

	Day 1												
Procedures	Pre- dose	0	5m	15m	30m	1h	1.25h	1.5h	2h	4h	6h	8h	12h [a]
Tiotropium/olodaterol dosing by Respimat®		X											
RPL554 or placebo dosing by nebulization		X											X
Brief physical examination	X												
Vital signs	X				X	X			X	X	X	X	X
12-lead ECG	X								X	X			
Spirometry	X[c]		X	X	X	X		X	X	X	X	X	X
Inhalation training	X												
Whole body plethysmography	X						X						
Randomization [b]	X												
Urine pregnancy test (females of childbearing potential)	X												
Dyspnea scale	X		X	X	X								
Adverse events					•		Throu	ıghout					•

Abbreviations: ECG=electrocardiogram; h=hours (post-dose); m=minutes (post-dose)

NOTE: Table 4 (Days 2 through 4) continues on next two pages.

Verona Pharma plc CONFIDENTIAL Page 32 of 66

[[]a] Post-dose measurements will be taken in relation to the morning dose of tiotropium/olodaterol and RPL554 or placebo. The 12-hour procedures will therefore be performed pre-dose before the evening dose of RPL554 or placebo

[[]b] Treatment Period 1 only

[[]c] Performed at 1 hour and immediately pre-dose

Due on during	Day 2														
Procedures	Pre-	0	15m	30m	1h	1.25h	2h	3h	4h	12h [a]					
Tiotropium/olodaterol dosing by Respimat®		X													
RPL554 or placebo dosing by nebulization		X								X					
Vital signs	X			X	X		X	X	X	X					
12-lead ECG	X						X								
Spirometry	X		X	X	X		X	X	X	X					
Adverse events	Throughout														

Abbreviations: ECG=electrocardiogram; h=hour; m=minutes

Verona Pharma plc CONFIDENTIAL Page 33 of 66

[[]a] Post-dose samples will be taken in relation to the morning dose of tiotropium/olodaterol and RPL554 or placebo. The 12-hour procedures will therefore be performed pre-dose before the evening dose of RPL554 or placebo.

Procedures		Day 3															Day 4 [a]				
	Pre-	0	5 m	15m	30m	45m	1h	1.25h	1.5h	2h	4h	6h	8h	8.25h	12h	12.25h	13 h	14h	16 h	23 h	24 h
Tiotropium/olodaterol dosing by Respimat®		X																			
RPL554 or placebo dosing by nebulization		X													X						
Brief physical examination																					X[b]
Vital signs	X				X		X			X	X	X	X								X
12-lead ECG	X									X											X
24-hour Holter monitor placed	X																				
Spirometry	X		X	X	X		X		X	X	X	X	X		X		X	X	X	X	X
Whole body plethysmography	X							X						X		X					
Pharmacokinetic samples	X		X		X	X	X		X	X	X		X		X ^c						
Hematology and biochemistry																					X
Dyspnea scale	X		X	X	X																X
Adverse events										T	hrougho	out									

Abbreviations: ECG=electrocardiogram; h=hour; m=minutes

- [a] Procedures performed prior to discharge from the study center on the morning of Day 4, 12 hours after final RPL554 dosing on Day 3
- [b] Can be performed any time prior to discharge
- [c] Perform pharmacokinetic sample prior to dosing

Verona Pharma plc CONFIDENTIAL Page 34 of 66

